Adherence is a key factor in the potential effectiveness of the treatment of chronic conditions in patients. According to the World Health Organization, however, 50 per cent of these patients do not comply with the drug regime in developed countries(1). In developing countries, access to health services is limited and there is a shortage of health care providers and financial resources, so it is assumed that this number is higher. Medication non-adherence is often linked to adverse clinical results (2) and decreased quality of life (3)and higher use of health resources(4). Drug non-adherence is widespread among the elderly, and over 55% live with multiple diseases (i.e., multiple chronic diseases) together(5). In addition to the high complexity of multi-morbidity, patients are more likely to receive complex medications(6) , adverse drug reactions(7), and substantial drug burdens (8). Patients need to spend a lot of energy and time taking and administering medicines(9, 10). Multi-morbidity is an obstacle to the self-management of drugs that lead to disease, leading to poor compliance and treatment results(11, 12) . Support for the self-management of medications is an effective strategy for addressing the challenges of taking medications and giving patients the opportunity to take care of themselves. In general, medication self-management programs integrate multiple components to help patients take drugs efficiently and safely, such as changes in health behavior change, patient education, shared decision making, and goal setting. Drug self-management interventions have been established in several conditions(13-15). However, Current clinical trials focus on specific diseases or drugs, limiting their generalization to older patients with multiple diseases(16, 17). Some studies have found the effectiveness of self-management interventions in this complex patient group(18-21) . Unfortunately, most have not significantly improved compliance and health outcomes. A six-month self-management support program for the treatment of multiple diseases based on cognitive behavioral therapy and motivational interviews did not result in any improvements in the outcome of patients, except for self-assessment of health(18). Another personalized self-management intervention by nurses in patients with coronary disease and depression also did not show significant differences in compliance and health outcomes between the intervention and the control group(19) . One explanation is that most self-care programs for elderly patients with multiple diseases are designed to address all aspects of self-care, but not specifically to improve medication self-management capacity or focus on patients with adherence problems. A study by Cochrane concluded that interventions were more effective in targeting specific problems experienced by multi-morbidity patients., such as depression, functional limitation, and non-adherence to medication non-adherence(22) . Interventions with a broader focus, such as case management and changes in treatment for multi-morbid patients, seem to be less effective. Drug management interventions are more effective in addressing specific problems related to the use of drugs. Information about the need to move health education intervention way from the tradition information based and advice-giving model to health coaching using evoking, focusing, planning and motivational interview process. Furthermore, the social behavior model was rarely used to guide study design and explain the mechanisms of previous studies underlying important or non-significant intervention effects. Therefore, although interest in the study of adult patients with multiple diseases is growing, promoting medication adherence of this group of patients is still a challenge for healthcare providers and researchers(23). Information about the need to move health education intervention way from the tradition information based and advice-giving model to health coaching using

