
evoking, focusing, planning and motivational interview process. The current study aims to implement evidence-based, theoretical and nurse-led drug self-management interventions in adult patients with multi-morbidity.

4. Objectives

The primary objective

To evaluate the effectiveness of a six-week intervention led by a nurse in medication self-management to improve medication compliance in adult patients with multimorbidity and going to discharge, as compared with standard care.

[figure not shown]
Secondary objectives

To evaluate the effectiveness of the intervention on the improvement of patients' medication self-management capacity (medication knowledge, medication beliefs, and medication self-efficacy), treatment experiences (medication treatment satisfaction and treatment burden), as compared with standard care. *(Retrospective means the data is already in existence when the project is submitted to the IRB for initial (if this is a retrospective chart review, the end date must come before the submission date): mm/dd/yyyy to mm/dd/yyyy)*

5. Study Methodology

This is a single Centre open label, two-arm randomized controlled trial with 1:1 randomization at the participant level. The patient population will be patients with at least two comorbidities. The patient recruitment will be done in the National Centre for Cancer Care and Research (NCCCR) in the outpatient department in the clinical nurse specialist counselling room. Participants will randomly be allocated to receive standard care(control) and standard care plus the medication self-management intervention (Motivational Interview). Primary and secondary outcomes of study will measure better medication adherence, medication self-management capacity and treatment experiences, which will be collected from both group including the intervention group and control group (Participants in the control group will continue to receive all respects of standard care offered by healthcare providers) at baseline (T0), in the 7th week immediately post-intervention (T1), and at 3-month post-intervention (T2). This protocol is presented based on the recommendations of the Standard Protocol Items: Recommendations for Interventional Trials (SPIRIT) 2013 statement(24). The results of this trial will be reported as per the Consolidated Standards of Reporting Trials (CONSORT) 2010 statement(25).

An overview of the study design is shown in Fig. 1.

[figure not shown]

Fig. 1 CONSORT flow diagram of the study protocol

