
2nd face-to-face education session
 
 To help patients change negative attitudes and beliefs about medication treatments and become motivated to it. 	
(1) Give patients the opportunity to understand the importance of medication adherence and the consequences of non-adherence.
 
(2) Encourage patients to express feelings and barriers to family members and seek assistance, where appropriate. (3) Provide a list of local resource information to patients (e.g., medical care institutions, psychological support organizations, and peer support teams).
	
 ❖ Motivational interviewing

3rd face-to-face education session
 
 To help patients develop skills and strategies to overcome practical barriers of their medication treatments. To help patients set goals and develop a workable adherence improvement plan. 	
(1) Nurses will educate patients about six skills in medication self-management:
 
 Identifying and coping with medication side effects; Incorporating medication treatments into daily life; Obtaining and updating medication adherence-related information; Acquiring, self-cueing and self-administering medications; Effectively communicating with healthcare providers; Acquiring social and instrumental support for adherence. 
(2) Ask patients to select three skills they most want to learn or help most to take their medications; Discuss with patients
	
 ❖ Planning coping responses ❖ Goal setting

about strategies on how to apply the three skills to their self-management.

(3) Set goals and help make an individualized adherence improvement plan based on patients' expectations and preferences.

(1) Ask whether patients can adhere to the medications in the last week and if not, the reasons for medication non-adherence will be asked and discussed with patients.

2-week Telephone follow-

- To further explore the challenges and difficulties in medication self-management.
- To provide feedback and suggestions according to patients' performance.

(2) Ask whether patients can apply skills in medication self-management and encounter any challenges and concerns in medication-taking.

(3) Further adherence education where needed.

(4) Conclude what is discussed and encourage patients to contact healthcare providers when they have adherence problems

- ❖ Active listening

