Based on screening & randomization tool

Risk

In this section describe the anticipated risks associated with participation in the research (i.e. illness, injury, death)

No risk is anticipated as part of study

Bio-Specimens & Sample Collection

In this section describe what specimens or samples will be collected specifically for research, if specimens will be stored long-term and/or destroyed. Consider what happens to data/specimens if subject withdraws consent

NA

Outcomes

In this section provide details on the outcome measures and the anticipated primary & secondary outcomes

Outcome assessment

The nurses masked to the participant allocation will collect follow-up data through telephone interview. Participants will be assessed at baseline (T0), in the week immediately post-intervention (7th week) (T1), and at 3-month post-intervention (T2). Table 2 provides an overview of primary and secondary outcomes as well as covariates at each time point. Permission will be obtained from the original authors to use the scales for this study.

Primary outcome

Medication Adherence

The English version of Morisky-8 will be administered to assess medication adherence of the participants(29). The Morisky-8 is a self-reporting measure of unintentional and intentional medication non-adherent behaviors with a yes and no response. The total score of the moresky-8 ranges from 0 to 8, with a higher score representing higher adherence to medication.

Table 2 Schedule of enrolment, interventions, and assessments

TIMEPOINT	STUDY PERIOD				
	Enrolment	Baseline T0	Intervention	Follow-up	
				T1	T2
ENROLMENT					
Eligibility screen	X				
Informed consent	X				
Allocation		X			
INTERVENTION					
Intervention group			X		
Control group			X		
ASSESSMENTS					
Primary outcome					
Medication adherence (Moresky-8)		X		X	X
Secondary outcomes					
Medication knowledge (PKMUQ)		X		X	X
Medication beliefs (BMQ)		X		X	X
Medication self-efficacy (SEAMS)		X		X	X
Treatment burden (TBQ)		X		X	X
Potential covariates					

Socio-demographics questionnaire)	(Patients	X
Number of prescribed medications (one-item question)		X
Depressive symptoms (PHQ-9)		X

Secondary

outcomes

Medication Knowledge

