Our primary analysis will be the ‘intention-- to-treat’ population, which will include all randomized patients analyzed according to their original treatment allocation, irrespective of their subsequent adherence or how they were actually treated. All data will be analyzed using STATA 17.0 software. Descriptive statistics will be used to describe and compare socio-demographic data on participants between the intervention and control group. Continuous variables that follow a normal distribution will be expressed as means and standard deviations, whereas categorical variables will be presented as frequency counts and percentages. Median values and interquartile ranges will be calculated for continuous data with a skewed distribution. Mann-Whitney U-test or t-test will be performed for continuous data to compare baseline characteristics between groups, and Chi-squared test or Fisher’s exact test will be used for categorical variables. The distributions of the outcome variables will be evaluated, and normalizing transformation will be applied as needed. Primary and secondary outcomes will be analyzed following the intention to treat principle at the individual participant level. Changes in repeated outcome measures across different time points between the intervention and control group will be analyzed using generalized estimating equation models with adjustment for potential confounders of the baseline variables. All statistical tests are two-sided, and $p < 0.05$ will be statistically significant.

9. Adverse Event Reporting

In this section, provide a definition of anticipated adverse events that are related to the research, including a description of how SAEs will be assessed, tracked and reported

There will not be any adverse events related to intervention because it is educational intervention. If some adverse event related to outcome reported during the study, we will notify to the IRB.

10. Ethical Consideration

A statement that the study will be conducted in full conformance with principles of the “Declaration of Helsinki”, Good Clinical Practice (GCP) and within the laws and regulations of MoPH in Qatar.

The study will be conducted in full conformance with principles of the “Declaration of Helsinki”, Good Clinical Practice (GCP) and within the laws and regulations of MoPH in Qatar.

11. Sponsor, Funding & Collaborator Information

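### Intervention-related adverse events are ruled out in advance and harms are not solicited in either arm, although the trial aims to raise medicine-taking in patients the protocol describes as prone to adverse drug reactions

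*Combined protocol and SAP*

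**What the plan says.** Section 9 (Adverse Event Reporting) contains two sentences of substance. The first is "There will not be any adverse events related to intervention because it is educational intervention". The second is "If some adverse event related to outcome reported during the study, we will notify to the IRB". The template prompt printed above them asks for a definition of anticipated events, "including a description of how SAEs will be assessed, tracked and reported"; the text does not answer it. The Risk entry in Section 7 reads "No risk is anticipated as part of study".

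Elsewhere the protocol says of multimorbidity that "patients are more likely to receive complex medications(6) , adverse drug reactions(7), and substantial drug burdens (8)" (Section 3). The primary objective in Section 4 is "to improve medication compliance in adult patients with multimorbidity and going to discharge, as compared with standard care", and Section 6 restricts entry to patients with low adherence. Table 1 puts side effects into the session 1 adherence checklist and education, and lists "Identifying and coping with medication side effects" among the six skills of session 3.

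**The concern.** The intervention is educational, but it is meant to act through drug exposure: patients who were not taking their medicines are to take more of them. If it succeeds, the frequency of drug reactions could change as a consequence. Section 9 settles that question by assertion. Read literally, it classes every event as unrelated before any has been seen.

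Two things are at stake. First, the trial could not describe whether a gain in adherence came with more drug-related harm, which anyone deciding whether to run a larger trial would want to know. Second, events that do come to light would arise from contacts that differ between arms, so an informal count would not be a fair comparison.

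**Working it through.** The plan gives no safety figure to reproduce, so the check is mainly a reading of every place where harms could be recorded.

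**Step 1. Is there any systematic collection?**

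- Table 2 (schedule): adherence, knowledge, beliefs, self-efficacy, treatment burden and baseline covariates. No item on adverse events or drug reactions at T0, T1 or T2.
- Outcome descriptions (Section 7): the beliefs questionnaire covers concerns about medicines and the burden questionnaire covers difficulty with treatment. Neither is described as counting events.
- Intervention logbook (Intervention fidelity and contamination): number, duration and date of sessions only.
- Section 8 (analysis): no summary of harms.
- Section 14 (appendices): four forms, namely screening and randomization, Morisky, BMQ and SEAMS. None is for adverse events.
- Section 9: IRB notification if an event tied to the outcome happens to be reported. No definition, time window, assessor or seriousness grading.

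So collection is passive only.

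**Step 2. Where could side effects come up, by arm?**

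- Session 1: yes, in the checklist and the education. Intervention arm only.
- Session 2: not mentioned in its content.
- Session 3: yes, as one of six skills, from which patients choose three to work on. Intervention arm only.
- Written materials after the last session: include side effects of each usual chronic medicine. Intervention arm only.
- Two telephone follow-ups: side effects are not named, but challenges and concerns with taking medicines are invited. Intervention arm only.
- Controls: physician consultations and education at clinic visits, and scheduled physician telephone follow-up for those with hypertension or diabetes. No structured session.
- T1 and T2 interviews by masked nurses: both arms, but without a harms question.

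Side effects are therefore named in two of the five intervention contacts and in no structured trial contact for controls. The direction of any imbalance in ascertainment is plausible; its size is unknown.

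**Step 3. What could this sample size show if harms were asked about?**

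Input: 100 participants randomized about 1:1 (Section 6), so 100 / 2 = 50 per arm; 47 per arm if only the 94 completers of the sample size statement are counted.

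- Upper limit with zero events: solve (1 − p)^n = 0.05, giving p = 1 − 0.05^(1/n). For n = 50, 1 − 0.05^(1/50) = 0.058, or 5.8%. For n = 47, 1 − 0.05^(1/47) = 0.062, or 6.2%.
- Chance of at least one event in an arm of 50: 1 − (1 − p)^50. The documents give no event rates, so these are assumed: p = 1% gives 39.5%, 2% gives 63.6%, 5% gives 92.3%, 10% gives 99.5%.

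Reactions affecting 5% or more of patients would very probably appear at least once per arm if solicited; events at 1% could easily be missed.

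**The case against.** The strongest reply is that the drugs cause reactions, not the education, and that both arms are prescribed drugs by their physicians. The background also links non-adherence to adverse clinical results, and the intervention includes reducing treatment burden and encouraging patients to discuss burdensome regimens with physicians. On the plan's own text the net effect on harm could go either way. This stands, and it is why the passages are in tension rather than in flat contradiction. But an open direction is a reason to ask about harms in both arms. It does not support declaring that none can be related.

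A second reply is that this is a feasibility trial of 100 patients with no safety objective, and that an IRB route exists. That also stands in part: it argues against a formal safety comparison, but not against a descriptive count.

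A reader might go further and infer any of the following, which the documents do not support:

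- That all five nurse contacts discuss side effects. Table 1 names them in two.
- That controls have no opportunity to report harms. They have physician contact, and the same T1 and T2 calls.
- That the trial will report a spurious severalfold excess of events in the intervention arm. No planned analysis compares events by arm, and any such ratio would simply return whatever reporting rates were assumed.
- That the intervention is harmful, or that the adherence result is compromised. Nothing in the plan points to either.

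**Conclusion.** The point holds as a gap in safety ascertainment that should be closed. The protocol excludes intervention-related events by assertion, solicits no harms in either arm, and leaves its own template question on serious events unanswered. As written, the trial could support no statement about safety: an absence of recorded events would mean only that none had been reported. The primary and secondary comparisons do not change.

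The consequence cannot be put as a number from the documents. The 5.8% limit assumes that all 50 patients in an arm are fully ascertained and that none has an event. It is a property of the sample size and would be the same after the fix; what the fix does is make such a limit interpretable. The conclusion rests on two readings: that better adherence means greater exposure to prescribed medicines, and that the listed schedule, logbook and forms are complete.

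**What to change.** 1. Replace the absolute statements under Risk and in Section 9 with a statement that drug-related events could change as adherence changes.
2. Add two questions to the T1 and T2 telephone interviews by masked nurses, with identical wording in both arms: one on new or worse side effects, one on unplanned hospital or emergency attendance, each since the last interview (at T1, since baseline). Add the items to Table 2 and to the list of forms.
3. Add to Section 8 one descriptive table of both items by arm, without a significance test.
4. Reword the IRB trigger so that it covers any reported serious event and no longer depends on a link to the outcome. State the definitions of adverse event and serious adverse event and the role responsible for assessment, as the section's prompt asks.

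The cost is slightly longer calls at two contacts already scheduled, plus one table. No visit is added, and treatment, sample size and primary analysis are untouched. The questions need to be in place before the first T1 call, because equal ascertainment cannot be recovered afterwards. One limit remains: patients taught to recognise side effects may report them more readily, so identical questions equalise the asking but not necessarily the answering. The table should carry that caveat.
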